### **8.2.12. All-Cause Mortality from Baseline through Day 28**

All-cause mortality will be analyzed using a time-to-event approach. Summaries will include the number of subjects experiencing the event (death) and the number of subjects censored; the median, lower quartile and upper quartile estimate of time-to-event; and point estimates for the mortality rates.

A Kaplan-Meier graph of mortality by treatment group will be presented.

The null hypothesis of no difference between varespladib-methyl and placebo will be tested using a Cox proportional hazard regression model with a categorical variable for the treatment arm as independent variable and adjusted for baseline SSS, age group, baseline neurotoxicity, and completion of initial dose of antivenom prior to initiation of study drug which will be presented together with two-sided 95% confidence intervals, as well as the corresponding P value.

All-cause mortality will be censored at Day 28.

If fewer than 5 subjects die, this analysis will not be performed. All deaths will be listed.

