5 INTRODUCTION

5.1 Background and Rationale

The treatment of snakebite envenoming is an urgent, global unmet medical need. It is estimated that worldwide more than 5 million snakebite envenomings occur annually, causing significant morbidity (approximately 400,000 causing permanent deformities or amputation) and mortality (up to 138,000 causing death) (Gutierrez, et al., 2017; Longbottom, et al., 2018). Snakebite primarily affects poor, rural populations in tropical and sub-tropical regions of developing countries, where outcomes are adversely impacted by the snakebite victim's lack of proximity and/or access to healthcare, including access to currently available antivenom therapies (Longbottom, et al., 2018). Although comparatively unusual in the U.S., snakebite envenoming incurs significant morbidity and occasional mortality with bad outcomes primarily associated with delays in care, young age, neurological deficit, thrombocytopenia and coagulation abnormalities (Gerardo, et al., 2019).

Approximately 5.8 billion people live in regions that place them at risk for being bitten by a medically important snake (Longbottom, et al., 2018) and it is estimated that > 75% of deaths from snakebite occur outside the hospital setting before victims can reach medical care. While not all snakebites result in envenoming with morbidity and mortality, often by the time patients receive the appropriate medical care in a hospital setting it is far too late and the toxicities of snakebite envenoming have substantially progressed and are no longer amenable to effective treatment by antivenom therapy (Vaiyapuri, et al., 2013; Gerardo, et al., 2019). To underscore the urgency of the global public health crisis posed by snakebite envenoming, the World Health Organization (WHO) recently classified snakebite envenoming as a neglected tropical disease (Longbottom, et al., 2018). Furthermore, the WHO's Snakebite Envenoming Working Group stated that "accelerating preclinical and clinical testing of promising prehospital adjunctive treatments, such as the phospholipase A2 inhibitor varespladib or varespladib-methyl, as part of the WHO snake bite envenoming research agenda may lead to early improvements in prehospital survival" (Williams, et al., 2019).

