### **6.1.2. Adjustments for Covariates**

The comparison of the primary and secondary efficacy endpoints between the varespladib-methyl and placebo groups for the primary efficacy analysis will be adjusted for four variables: (1) baseline SSS composed of the pulmonary, cardiovascular, hematologic, renal, and nervous system sections treated as a continuous variable; (2) age group treated as a dichotomous variable (age 5-17 vs. age  $\geq$ 18 years); (3) baseline neurotoxicity (SSS neurological system subscore) treated as a dichotomous variable (0-1 vs.  $\geq$ 2); and (4) Country (U.S. vs. India). Because we anticipate low numbers of patients in the two pediatric age group strata, we have collapsed these two strata into a single group (age 5-17) for the purpose of data analysis. A sensitivity analysis for the primary and key secondary endpoints will include a fourth covariate: completion of the initial dose of antivenom prior to initiation of study drug (Yes or No).

The mixed model for repeated measurements (MMRM) will be adjusted for baseline SSS, baseline neurotoxicity, age group, completion of the initial dose of antivenom prior to initiation of study drug, and scheduled timepoint of assessment. It will also include terms for treatment-by-time interaction and baseline score-by-time interaction.

The Cox model to estimate the hazard ratios for all-cause mortality will be adjusted for baseline SSS, baseline neurotoxicity, age group, and completion of the initial dose of antivenom prior to initiation of study drug.

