## 8.2. Other Secondary Efficacy Analyses

The other secondary efficacy analyses will be interpreted as exploratory analyses. All secondary endpoints will be analyzed according to the prespecified assessment timepoints listed in the protocol. Statistical models will include covariates for baseline SSS, baseline neurotoxicity (Yes, No; based on the SSS neurological system subscore), age group (5-17, 18+), and, when available, the baseline value of the particular endpoint unless otherwise specified below. A sensitivity analysis will include as a covariate yes/no completion of an initial dose of antivenom prior to randomization. The methods described here are what is currently planned. However, for each analysis, we will examine the distribution of the strata pooled over treatment and placebo. If the data are unlikely to support the planned analysis or if the model fails to converge, removal of covariates and different estimation routines will be attempted and described in the CSR.

### 8.2.1. Complete SSS from Baseline through Day 7

The complete SSS (all sub-sections including pulmonary, cardiovascular, hematologic, renal, nervous system, gastrointestinal, and local wound) from baseline through Day 7 after first dose will be summarized using descriptive statistics of observed values and changes from baseline.

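### The mortality Cox model may be run at one death per parameter, and the SAP names neither the P value nor a method for deaths confined to one arm

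*SAP*

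**What the plan says.** SAP 8.2.12 states that the null hypothesis of equal mortality is "tested using a Cox proportional hazard regression model with a categorical variable for the treatment arm as independent variable", and that the model is "adjusted for baseline SSS, age group, baseline neurotoxicity, and completion of initial dose of antivenom prior to initiation of study drug". SAP 6.1.2 lists the same covariates. The output is described only as results "which will be presented together with two-sided 95% confidence intervals, as well as the corresponding P value"; whether that P value is Wald, likelihood-ratio or score is not stated.

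The model has one cut-off: "If fewer than 5 subjects die, this analysis will not be performed. All deaths will be listed".

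The introduction to SAP 8.2 covers this analysis. It labels the other secondary analyses exploratory and provides for a look at the strata with the two arms pooled. It adds: "If the data are unlikely to support the planned analysis or if the model fails to converge, removal of covariates and different estimation routines" are to be tried and reported in the CSR. It gives no order of removal and names no routine.

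Protocol 13.1.4.5 planned only Kaplan-Meier methods for mortality. SAP 9.1.2 sends the safety analysis of mortality back to 8.2.12, and SAP 9 plans no inferential safety tests.

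**The concern.** The cut-off permits one death per estimated parameter. At such counts a Cox partial likelihood often has no maximum: some coefficient runs off to infinity and its standard error with it. When the treatment coefficient is the one affected, the result depends almost entirely on which P value the programmer reports. The data most favourable to one arm are also the data for which a Wald test says least.

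This section holds the only between-arm mortality test in the SAP, for benefit or for harm. The SAP's version history shows that the sponsor meant to deal with too few deaths for formal models; the chosen number does not achieve that.

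**Working it through.** **The plan's own figure.** The SAP states no power or expected count for mortality. Its only power figure, 94 patients for 85% on the primary endpoint (SAP 3.2), reproduces: 2 × (1.960 + 1.036)² × (1.75/1.1)² = 45.4, so 46 per arm or 92 in all. The noncentral t with 47 per arm gives 85.4%. This has no bearing on mortality.

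**Parameters per event.** Treatment 1, baseline SSS 1 (continuous), age group 1, neurotoxicity 1, prior antivenom 1: five in total. At the cut-off, 5 deaths / 5 parameters = 1.

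**How often the full model has no finite estimate.** This was simulated with 94 patients (repeated with 110 at 5, 8 and 10 deaths), 1:1, 400 trials per setting, so Monte Carlo error is at most about 2.5 points. The documents give no prevalences. Assumed: pediatric 10–30%, neurotoxicity 10–40%, prior antivenom 30–50%, log hazard ratio per SSS point 0 or 0.3, treatment hazard ratio 1 or 0.5.

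| Deaths | Any coefficient infinite |
|---|---|
| 5 | 31–84% |
| 8–10 | 3–61% |
| 15–20 | 0.3–28% |

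Most failures are in a covariate. For example, if 20% of patients are pediatric and age is unrelated to death, the chance of no pediatric death among 5 is 0.8⁵ = 33%. The treatment coefficient was infinite in only about 4–15% of trials at 5 deaths.

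**Chance that all 5 deaths fall in one arm.** With hazard ratio h, each death falls on active with probability about h/(1 + h).
- h = 1: 2 × 0.5⁵ = 6.25%.
- h = 0.5: (1/3)⁵ + (2/3)⁵ = 13.6%.

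**What a one-arm split yields (treatment-only model).** With n per arm and D deaths, all in one arm, the likelihood-ratio statistic is 2 Σ ln[(2n − k)/(n − k)], k = 0 to D − 1.

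| Split | Wald P | Likelihood-ratio P | Log-rank P | Fisher P |
|---|---|---|---|---|
| 0/47 v 5/47 | 0.994 | 0.0075 | 0.022 | 0.056 |
| 0/47 v 6/47 | 0.993 | 0.003 | 0.012 | 0.026 |
| 0/55 v 6/55 | 0.999 | 0.003 | 0.012 | 0.027 |

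The Wald entries are artefacts of where the iteration stops. In the first row it stopped at log hazard ratio −18.2 with SE 2,434, so z = −0.0075. In the third it stopped at −23 with SE 27,000. For the third row the profile-likelihood upper limit for the hazard ratio is 0.36, whereas a Wald interval runs in effect from 0 to infinity.

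**Does the SAP 8.2 fallback cure the split?** No. Removing all four covariates gives exactly the table above. A look pooled over arms cannot show a split between arms. The fits above met their stopping rule, so a non-convergence trigger may not fire.

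**Chance of reaching 5 deaths.** The documents give no in-hospital mortality rate. Protocol 5.1 gives up to 138,000 deaths per 5 million or more envenomings (2.76%) and says "it is estimated that > 75% of deaths from snakebite occur outside the hospital setting before victims can reach medical care"; a quarter of 2.76% is 0.69%. With 110 patients and Poisson counts:
- 0.69%: 0.76 expected deaths, P(5 or more) = 0.1%.
- 2.76%: 3.04 expected, 19%.
- 5% (assumed): 5.5 expected, 64%.

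Because a one-arm split becomes rarer as deaths increase, the chance of reaching 5 deaths and finding all in one arm is at most 0.19 × 0.0625 = 1.2% (h = 1) or 0.19 × 0.136 = 2.6% (h = 0.5) at the 2.76% rate, and at most 4.0% or 8.7% at the 5% rate.

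**The case against.** Several points on the other side stand.

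- The analysis is exploratory and outside the alpha-protected sequence, so no confirmatory claim depends on it.
- A mortality difference would not be hidden. SAP 9.1 tabulates fatal treatment-emergent events by arm with no minimum count, all deaths are listed, the DSMB sees safety summaries by group (Protocol 12), and deaths before the 9-hour assessment enter the primary endpoint at the worst score (SAP 6.1.7.1).
- Exact testing gains little at the lowest counts. Fisher's best P with 55 per arm is 0.12 at 4 deaths and 0.057 at 5.
- The fallback is broader than non-convergence, and its reference to other routines leaves room for penalised or exact methods.

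Three stronger readings are tempting, and the documents do not support them. A reader might infer that a one-arm split would be reported as P close to 1; that follows only if the Wald P is used, and SAP 8.2.12 names none. A reader might infer that the treatment effect is lost whenever the full model fails; in most simulated failures it stayed finite. A reader might take 0.7–2.8% as in-hospital mortality on the protocol's own figures. The denominator includes envenomings that never reach hospital, and the trial selects patients by severity, so neither end is a bound.

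What remains is that the fallback names no method and no order of removal, and that removing covariates does nothing for a one-arm split.

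**Conclusion.** The concern holds in a limited form. The 5-death cut-off is too low for a five-parameter Cox model, and the SAP leaves open a choice that can turn the same 0 versus 6 data into P = 0.003 or P of about 0.99. The parameter count, the unnamed P value and the failure of covariate removal to cure a one-arm split follow from the text and from algebra. The 31–84% rests on assumed prevalences, and the chance of reaching 5 deaths (0.1% to 64%) on assumed mortality. A one-arm split with 5 or more deaths is an uncommon outcome. Given that, and the exploratory status, this is a cheap improvement rather than a threat to the trial's conclusions.

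**What to change.** Amend SAP 8.2.12 and the matching sentence in 6.1.2 before unblinding:

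1. At any number of deaths, report Day 28 deaths by arm with an exact confidence interval for the risk difference and one named P value, exact or log-rank.
2. Take the hazard ratio from a treatment-only Cox model with Firth's penalised likelihood and a profile-likelihood interval, not a Wald interval.
3. Fit the covariate-adjusted model only above a prespecified minimum number of events per parameter, with the reason for that minimum stated.

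The cost is a few lines of SAP text and code. The low-count hazard ratio would be unadjusted, and a Fisher-type exact test is conservative: it cannot reach 0.05 at 5 or fewer deaths.

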### **8.2.13. Clinical Global Impression–Improvement (CGI-I) from Baseline through Day 7**

CGI-I (1-7 scale) will be treated as a continuous variable and summary statistics will be reported at each visit and depicted graphically showing mean scores for each treatment group over time. CGI-I scores from baseline through day 7 will be compared using MMRM, with treatment as the variable of interest, with baseline SSS, age group, baseline CGI-I score, and baseline neurotoxicity as covariates. The model will be used to estimate the effect of treatment on CGI-I scores at each assessment time point through Day 7.

Secondarily, CGI-C will be dichotomized into subjects who are responders (score of either 1 – very much improved; 2 – much improved) vs. non-responders (scores of 3-7). The proportion of responders within each treatment group will be compared with logistic regression including the same covariates described above.

### **8.2.14. Patient Global Impression of Change (PGI-C) from Baseline through Day 7**

PGI-C (0-10 scale) will be treated as a continuous variable. Means and standard deviations will be tabulated at each visit and graphically for each treatment group over time. PGI-C scores from baseline through day 7 will be compared using MMRM, with treatment as the variable of interest, and baseline SSS, age group, baseline PGI-C score, baseline neurotoxicity, and visit, and treatment by visit interaction as covariates. The MMRM approach will be similar to the model described in [Section 8.2.1](#). LS means and changes after baseline will be calculated from the model at Day 7. Logistic regression will also be used to compare PGI-C responders by treatment group at each visit through Day 7. A responder is defined as a PGI-C score of 3 or lower.

### **8.2.15. Patient-Specific Functional Scale (PSFS) Total Score through Day 28**

PSFS (0-10 scale) will be treated as a continuous variable. The means and standard deviations will be tabulated at each visit and depicted graphically for each treatment group over time. PSFS scores through day 28 will be compared using MMRM, with treatment as the variable of interest, and baseline SSS, age group, baseline neurotoxicity, and visit, and visit by treatment interaction as covariates. The MMRM approach will be similar to the model described in [Section 8.2.1](#). The model will be used to estimate the effect of treatment on PSFS scores at each assessment time point through Day 28.

## **8.3. Exploratory Efficacy Analysis**

The ITT population will be used for the exploratory analyses.

### **8.3.1. Change in the SSS from Baseline through Day 7 Using Compressed SSS Scale**

The compressed SSS as well as the 6hr and 9hr mean scores will be calculated by first subtracting 1 from non-zero responses to the pulmonary, cardiovascular, hematologic, renal, and nervous system sections of the SSS. The sum of the adjusted values of the 5 subsections will be the total SSS used to calculate the compressed score. The endpoint will be the change from baseline through Day 7 compressed scores: Change = Baseline – Score (at each time).

Descriptive statistics for the compressed SSS scores will be tabulated by treatment group.

The change from baseline to the average of the 6hr and 9hr of the compressed SSS will be presented by treatment group within an analysis of covariance model (ANCOVA) with the baseline SSS score, age group, the presence or absence of baseline neurotoxic symptoms as covariates.

### **8.3.2. SSS from Baseline through Day 28 After First Dose**

The SSS from baseline through Day 28 post-initial dose will be summarized using descriptive statistics of absolute values and change from baseline at each time point and depicted graphically.

When more than one SSS assessment falls within the same time window, then only the SSS assessment closest to the middle point of the time window will be assigned to the time point. In case of values that are equidistant to the middle point, the latest assessment only will be assigned to the time point.

### **8.3.3. Grip Strength Pre-Dosing through Day 28**

Descriptive summaries of absolute value and change from the baseline of grip strength will be tabulated by treatment group and visit and depicted graphically.

### **8.3.4. SSS Neurologic System Subscore from Baseline through Day 7**

Descriptive summaries of absolute value and change from the baseline for the SSS neurologic system subscore will be tabulated by treatment group and visit from baseline through Day 7 and depicted graphically.

### **8.3.5. Analgesic Use through Day 28**

The number and proportion of subjects reporting (1) any analgesic and (2) any opioid use will be tabulated by treatment group and time point.

### **8.3.6. Clinical Global Impression – Improvement (CGI-I) from Baseline through Day 28**

Descriptive summaries of absolute value and change from baseline of CGI-I will be tabulated by treatment group and visit and depicted graphically.

### **8.3.7. Patient Global Impression of Change (PGIC) from Baseline through Day 28**

Descriptive summaries of absolute value and change from baseline of PGIC will be tabulated by treatment group and visit and depicted graphically.

### **8.3.8. Complete Blood Count (CBC) Laboratory Tests through All SSS Evaluation Days**

The number of subjects with CBC laboratory values below, within, or above the normal range by visit and in relation to baseline will be tabulated for key clinical CBC laboratory analytes: white blood cell count, hemoglobin level, platelet count (shift table). Denominator of the percentages will be the number of subjects in the ITT Population.

### **8.3.9. Transfusion Requirement from Baseline through Day 28**

The transfusion requirement will be assessed using the following indicators.

- Time to Hb stabilization
- Patients having transfusion event
- Time to first transfusion
- Total number of transfusions per subject
- Total blood units administered

Number and percentage of subject with a transfusion event will be described in summary tables by treatment arm and visit. Summary statistics of the total number of transfusions and the total blood units required will be presented in tables by treatment arm and visit for subject having a transfusion event.

Time to hemoglobin (Hb) stabilization and time to first transfusion will be analyzed using a descriptive time-to-event approach. Summaries will include the number of subjects experiencing the event and the number of subjects censored; the median, lower quartile and upper quartile estimate of time-to-event.

### **8.3.10. C-reactive Protein (CRP) from Baseline through Day 14**

The absolute values and change from baseline of CRP test results will be tabulated by treatment arm and visit.

### **8.3.11. D-dimer Levels from Baseline through Day 14**

D-dimer test results will be displayed in the data listings. Values outside the normal range will be

flagged, along with corresponding normal ranges.

### **8.3.12. Levels of Myonecrosis Marker (CK) from Baseline through Day 3 in Subjects Presenting with and without Tourniquets at Enrollment**

The analysis described in [Section 8.2.5](#) will be repeated for subjects:

- with tourniquets at enrollment
- without tourniquets at enrollment

Only subjects with  $CK \geq 2x$  institutional reference range at baseline will be included in the analysis.

### **8.3.13. Secretory Phospholipase A2 (sPLA2) in Serum at Specified Timepoints on Days 1 to 7 in All Subjects**

Descriptive summaries of absolute values and change from the baseline of sPLA2 levels will be tabulated by treatment group and visit and depicted graphically.

All sPLA2 from pre-dosing to Day 7 will be presented and used to (1) calculate maximum concentrations in both treatment groups, (2) compare concentration-time curves using a nonlinear regression to quantify a change in the half-maximal effective concentration (EC50) and its confidence interval, and (3) to compute a *p*-value that tests the null hypothesis that there is no difference between curves.

sPLA2 analysis will be performed by a third-party central lab. The analysis of sPLA2 will focus on enzyme activity. If available, another analysis will examine sPLA2 mass.

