10.2 Study Periods and Visits

10.2.1 sPLA₂ and Pharmacokinetics Sample Timing

Note that the sPLA₂ and PK sample collection will be performed with a different timing than the other assessments, as described in the Schedule of Events (Table 1).

Specifically, PK sampling will only be performed for a subset of adult and pediatric subjects on Days 1 and 3 and all subjects on Day 7 as described in Section 10.3.2.1. Subjects will be enrolled for PK analysis as follows: Day 1 - 20 subjects, pre-dose and 0.5, 1, 2, 4, 6, 8, and 12 (pre-second dose) hours; Day 3 - 20 subjects, pre-dose and 0.5, 1, 2, 4, 6 hours; Day 7 - all subjects, pre-dose. Special attention should be paid to collection of PK samples on Day 1 of this protocol.

sPLA₂ sampling will be performed for all subjects on Day 1 (pre-dose and 1, 3, 6, and 9 hours post-first dose), and on Day 2, Day 3, and Day 7 (pre-dose).

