10.3.2 Pharmacokinetics

10.3.2.1 Pharmacokinetic Analysis Methods

The concentration of varespladib-methyl in plasma will be evaluated in a subset of both adult and pediatric subjects on Days 1 and 3 and in all subjects on Day 7. PK sampling will only be performed for a total of 20 adult and pediatric subjects on Days 1 and 3, and all subjects on Day 7. Once 20 subjects have provided PK samples for Days 1 and 3, sites will be notified by the

OPX-PR-01

sponsor to discontinue Day 1 and 3 PK sampling. Efforts will be made to include at least 4 pediatric subjects from each age tier (5 to < 11, 11 to < 18 years old) in the PK analysis. PK samples will be collected on Days 1 and 3 as follows:

- Day 1 (20 adult and pediatric subjects): pre-dose and 0.5, 1, 2, 4, 6, 8, and 12 (pre-second dose) hours post-dose.
- Day 3 (20 adult and pediatric subjects): pre-dose and 0.5, 1, 2, 4, and 6 hours post-dose.
- Day 7 (all 110 subjects): pre-dose.

The PK characterization of drug concentrations for each dose to be profiled will use noncompartmental analysis (NCA). Additional details of the parameters and their calculation and evaluation is included in the Statistical Analysis Plan (SAP).

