13.1.4.6 Exploratory, Corroborative, Sensitivity, and Other Analyses

Exploratory endpoint efficacy data will be summarized descriptively by visit within treatment groups.

Endpoints will also be analyzed in the subset of study participants who are enrolled prior to the completion of the first dose of antivenom and in the subset of study participants who are enrolled after the completion of the first dose of antivenom. Additional details will be provided in the SAP.

All sPLA₂ from beginning of IP dosing to discharge will be presented and used to calculate maximum concentrations in both treatment groups and compare concentration-time curves using a nonlinear regression to quantify a change in the half-maximal effective concentration (EC₅₀) and its confidence interval, and to compute a p-value that tests the null hypothesis that there is no difference between curves.

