Individual plasma concentration plots and mean data graphs will be produced using both linear and semi-logarithmic scales. Mean data graphs will show plasma concentration profiles by treatment group. Pharmacokinetic parameter estimates and summaries will be completed for the subjects in the PK population.

Exploratory analysis to correlate PK endpoints with sPLA2 activity may be conducted and documented in a separate analysis plan.

The PK analyses will be performed by a third-party central lab.

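### SAP 8.3.13 plans an EC50 from sPLA2 curves over time; a fit against time yields a half-time or rate, so the parameter is mislabelled, and its P value tests a different, incompletely specified null

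*SAP*

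**What the plan says.** SAP 8.3.13 begins with summaries of sPLA2 levels and changes from baseline by arm and visit, in tables and graphs. It then uses all values from pre-dosing to Day 7 for three things: peak levels per arm; a plan to "compare concentration-time curves using a nonlinear regression to quantify a change in the half-maximal effective concentration" with its confidence interval; and a P value that "tests the null hypothesis that there is no difference between curves". The measured quantity is sPLA2: the analysis "will focus on enzyme activity", with mass as a second analysis if available.

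Protocol 13.1.4.6 asks for the same regression and says it will "compute a p-value that tests the null hypothesis that there is no difference between curves", over a window from the start of dosing to discharge. The same section opens by saying "Exploratory endpoint efficacy data will be summarized descriptively by visit within treatment groups".

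On the data behind it, Protocol 10.2.1 states that sPLA2 "sampling will be performed for all subjects on Day 1 (pre-dose and 1, 3, 6, and 9 hours post-first dose"), plus Days 2, 3 and 7. For drug levels, Protocol 10.3.2.1 states "PK sampling will only be performed for a total of 20 adult and pediatric subjects on Days 1 and 3", with one pre-dose sample on Day 7 in everyone. SAP 11.1 says that an analysis relating PK endpoints to sPLA2 "activity may be conducted and documented in a separate analysis plan".

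**The concern.** An EC50 is the concentration that produces half of a maximal effect. Estimating it requires an exposure axis and an effect axis. SAP 8.3.13 supplies one measured variable, sPLA2, and a time axis. A change in EC50 between arms would also need one EC50 per arm, and the placebo arm has no drug concentration from which to obtain one.

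sPLA2 inhibition is the drug's proposed mechanism, and this is the trial's direct pharmacodynamic comparison. With no function, contrast or error model named, the person fitting the curve decides what is estimated, possibly after unblinding, and the result could be reported under a name that suggests a potency estimate.

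**Working it through.** The documents give no figure for this analysis, so there is none to reproduce. The check is first one of definition, then an illustration on assumed values.

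**What is paired with what**
- Vertical axis: sPLA2 activity, or mass (SAP 8.3.13).
- Horizontal axis: eight sampling times, namely Day 1 pre-dose, 1, 3, 6 and 9 h, then Days 2, 3 and 7 (Protocol 10.2.1).
- Drug concentration: not used in 8.3.13. Serial levels exist for 20 subjects only. If those 20 split 1:1 as randomised (an assumption), about 20 × 1/2 = 10 received active drug.
- If sPLA2 itself were meant as the exposure, an effect variable would be needed, and 8.3.13 names none.

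**What a fit against time returns**

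Take an exponential decline, y(t) = A·exp(−kt) + c. Its half-maximal point is t½ = ln 2 / k. Multiplying every concentration by s changes A to sA and c to sc and leaves k alone, so t½ does not depend on the concentration scale and is not a concentration.

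With assumed values A = 10, c = 1 and t½ = 6 h, at nominal times 0, 1, 3, 6, 9, 24, 48 and 144 h:
- exponential fit: 6.0 h; with concentrations × 1000: still 6.0 h; with time in days: 6/24 = 0.25;
- four-parameter Hill fit, y = c + A/(1 + (t/T)^h): T = 6.2 h;
- Hill fit with h fixed at 1: T = 6.5 h.

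The same noise-free data thus give 6.0, 6.2 or 6.5 h depending on a function that the plan does not name.

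**What the P value tests**

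For this curve, equality of curves means A, k and c all equal, tested by F = [(RSS_common − RSS_separate)/3] / [RSS_separate/df]. With 47 subjects per arm and 8 samples each, df = 2 × 47 × 8 − 6 = 746. Equality of the half-maximal parameter means k equal only, tested by z = (log k₁ − log k₂)/SE. In 400 simulated trials per scenario, with residual SD 4 and all samples treated as independent in the fit, the rejection rates at 5% were:

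| Assumed truth | Curve test | Half-time test |
|---|---|---|
| No difference; errors truly independent | 4.75% | 5.0% |
| Same half-time; amplitude 10 vs 7 | 100% | 5.75% |
| No difference; between-patient SD 4 | 20.25% | 0.5% |

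The second row shows that the P value and the confidence interval can give opposite answers, because they address different questions. The third row has within-patient correlation 4²/(4² + 4²) = 0.5. It shows what happens if that correlation is ignored: too many rejections for the curve test and too few for the half-time test.

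**The case against.** The strongest reply is that EC50 is being used loosely for the midpoint of a fitted curve and that only the label is at fault. A curve can be fitted and two arms compared, the null for the P value is written down, and nothing in the testing hierarchy depends on it. SAP 8.3.13 already gives descriptive results by arm and visit, SAP 11.1 already points PK-sPLA2 work to a separate plan, and the efficacy tables and figures listed in SAP 13 contain no sPLA2 curve or EC50 output. Much of this stands, and it limits the point to the mislabelled parameter and the unnamed model. It does not make the text right: the term is spelled out in full, and a time is not a half-maximal effective concentration.

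Three stronger readings are tempting, and the documents do not support them.
- That the P value is for the EC50. The SAP attaches only the confidence interval to EC50; the P value belongs to equality of curves.
- That the analysis cannot be computed. The fits above show that a half-maximal parameter and a curve test can both be obtained.
- That the standard error is understated about 2.1-fold, from 8 × 110 = 880 points and √(1 + 7 × 0.5) = 2.12. This needs pooled points, and neither document says that samples are pooled as independent; nonlinear regression can be fitted per patient or with random effects. It also rests on one assumed correlation (0.2 gives √2.4 = 1.55, and 0.8 gives √6.6 = 2.57). It applies to a mean level, not to a half-time, and does not size the EC50 defect.

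It is also fair to say that a repeated-measures model changes what is estimated. Naming the curve, calling its midpoint a half-time and adding patient-level random effects would be a legitimate alternative.

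**Conclusion.** Wrong as written, and minor. A regression of sPLA2 on time by arm can give a half-time, a rate or an amplitude. It cannot give an EC50, and placebo subjects have no exposure from which to derive one. This needs no numerical assumption. The P value has a stated null, but it is a different one from the quantity given a confidence interval, and it lacks a curve function and a within-patient error model. Anti-conservatism of the curve test is conditional on samples being treated as independent, on which the documents are silent; the 20% rate is an illustration on assumed values, not an estimate for this trial.

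The reach is one exploratory endpoint outside the fixed sequence in SAP 8.1.2. No primary or key secondary inference is touched.

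**What to change.** Delete EC50 from SAP 8.3.13 and Protocol 13.1.4.6, and align the two data windows (pre-dosing to Day 7 in one, dosing to discharge in the other). In its place:
- Compare sPLA2 activity between arms with a named within-patient model, for example an MMRM on log activity with treatment, visit, treatment-by-visit and baseline, and state the contrast that carries the P value. The SAP already uses this class of model in 8.2.1.
- Set a rule for zero or unquantifiable activity before unblinding. The rule in SAP 11.1 covers plasma drug concentrations and sets low values to 0, which a log scale cannot take.
- Optionally, compare the baseline-to-Day 7 AUC of activity by ANCOVA.
- Reserve any EC50 for the exposure-response plan foreseen in SAP 11.1, in active-arm subjects with PK samples.

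The cost is wording only: same samples, same assays, no effect on sample size or on the testing sequence.
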